Each trial is conducted as a pragmatic, multicentre, randomized (1:1), single-blinded, clinical trial. Participants are randomized to receive either 1) spinal anaesthesia (SA) or 2) general anaesthesia (GA). Study data is gathered continuously during admittance. Study personnel is blinded to the allocation of the patients, but clinical personnel and the patients are not blinded, as this is not feasible given the interventions.

RCT SAGA UKA is conducted as a pilot trial exclusively at Copenhagen University Hospital Hvidovre. RCT SAGA THA and RCT TKA are conducted as multicentre trials at both Copenhagen University Hospital Hvidovre and Lillebaelt Hospital – Vejle.

RANDOMIZATION

Permutated block-randomization (4 or 6), stratified by centre for RCT SAGA THA and TKA, with allocation disclosed using non-transparent envelopes. A designated person, at Clinical Orthopaedic Research Hvidovre, Copenhagen University Hospital Hvidovre, with no other relation to the project is responsible for generating randomization sequences and preparation of the envelopes. Included patients are randomised at least three days before their planned surgery date.

SAMPLE SIZE

v. 1.0

The primary endpoint of the study is whether patients are able to be safely mobilized during a 5meter walking test within 6 hours of surgery. In previous studies safe mobilization was achieved after GA for 95% of THA and TKA patients, while it was only achieved for 30-45% of THA and TKA patients after SA. For this study we decided on a minimal clinically relevant difference in proportions of 30%. To detect a clinically relevant difference between 60% achieving safe mobilization in one group and 90% of achieving safe mobilization in the other group within 6 hours, would require 32 patients in each arm of each trial (95% confidence, 80% power). We aim to include 37 participants to each arm of each trial, to allow for a 15% dropout-rate in each trial.

- RCT SAGA UKA: 74 participants (37 SA and 37 GA) all from Copenhagen University Hospital Hvidovre.
- RCT SAGA THA: 74 participants (37 SA and 37 GA) from Copenhagen University Hospital Hvidovre (intended nr. participants = 38) and Vejle Hospital (intended nr. participants = 36).
- RCT SAGA TKA: 74 participants (37 SA and 37 GA) from Copenhagen University Hospital Hvidovre (intended nr. participants = 38) and Vejle Hospital (intended nr. participants = 36).

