Attitude towards anaesthesia type: Whether patients would like to receive similar anaesthesia for any following arthroplasty surgery.

Blood transfusions: Whether patients received blood transfusion.

Emergency room contacts, complications, readmission or mortality within 30 days of surgery.

ANALYSIS METHODS

The primary analysis aim is to assess whether the ability to be safely mobilized within 6 hours of hip and knee arthroplasty is different between the two anesthetic methods, GA and SA. The main hypothesis to be tested is that GA patients are more likely to be safely mobilized compared to SA patients within 6 hours of arthroplasty surgery. This will be assessed in the (mITT) population, defined as all patients having undergone the intended arthroplasty surgery, between the comparison groups (GA and SA) as allocated. Superiority of GA over SA in achieving safe mobilization within 6 hours of surgery will be claimed if a difference in proportions of 30% is found in favour of GA.

Main analysis of primary outcome: The proportion of patients able to be safely mobilized within 6 hours of surgery will be compared between intervention groups using a logistic regression model. A supporting model adjusted, including possible confounders such as age and sex, will also be conducted. Estimates from the analysis will be presented as odd-ratios and 95% confidence intervals, for both crude and adjusted models.

In case of cross-over cases, a per-protocol analysis with similar statistical methods will be conducted.

Key secondary continuous outcomes will be analysed using t-test or Wilcoxon rank-sum test depending on normality. Results from t-tests will be presented as differences in means and 95%

confidence interval. Results from Wilcoxon rank-sum tests will be presented as differences in medians and p-values. Key secondary dichotomous outcomes will be compared using fisher's exact test. A mixed-effect model accounting for repeated measures using patient ID as a random effect will be used to compare both 4 and 6 hours NRS scores for pain and PONV between the intervention groups.

Normality will be evaluated using quantile-quantile plots and histograms.

MISSING DATA

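### Randomisation in the THA and TKA trials is stratified by centre, but no stated analysis includes centre, so the tests and confidence intervals do not reflect the design

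*SAP*

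**What the plan says.** The SAP's Randomization section specifies "Permutated block-randomization (4 or 6), stratified by centre for RCT SAGA THA and TKA". Trial Design names two sites for those trials, and Sample Size plans 38 patients at Hvidovre and 36 at Vejle in each. The UKA trial has one site: "RCT SAGA UKA is conducted as a pilot trial exclusively at Copenhagen University Hospital Hvidovre".

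Under Analysis Methods, the proportions safely mobilised "will be compared between intervention groups using a logistic regression model". No covariate is named, and the same paragraph later calls this model crude. The only other model for the primary outcome is described as follows: "A supporting model adjusted, including possible confounders such as age and sex, will also be conducted".

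Key secondary outcomes are compared by t-test, Wilcoxon rank-sum test or Fisher's exact test. Pain and PONV scores also get a mixed model whose only named random effect is the patient. No analysis is described as stratified by or adjusted for centre.

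**The concern.** Blocking within centre keeps the arms nearly balanced on centre, so differences between centres largely drop out of the treatment contrast. A crude analysis still counts those differences in its standard error. If the centres mobilise patients at different rates, the crude test rejects less often than its nominal 5%, its interval covers more often than 95%, and power is lost. Each trial has only 74 patients and reports 95% intervals as its main result.

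A centre effect is plausible but not shown. Physiotherapists judge whether gait is stable and safe, which leaves room for local practice, and the SAP already uses a different urinary-retention threshold at Vejle. If centre is added only after the data are seen, the choice will look data-driven.

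**Working it through.** **Inputs from the SAP.** Two centres with 38 and 36 patients, 1:1 allocation, so 19 + 18 = 37 per arm; blocks of 4 or 6; design rates 60% and 90%; 95% confidence; 80% power. **Assumption.** The gap between centres, which the SAP does not give, so a range is shown.

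**1. The plan's own figure.** With a two-sided 5% level and no continuity correction, the mean proportion is 0.75 and

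n = [1.96·√(2·0.75·0.25) + 0.842·√(0.6·0.4 + 0.9·0.1)]² / 0.30² = 31.5, rounded up to 32 per arm.

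This matches the SAP. It assumes no centre structure.

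**2. Size of the unadjusted test, by formula.** Under the null, let centre rates be p₁ (19 per arm) and p₂ (18 per arm).

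- Pooled rate: p = (19p₁ + 18p₂)/37.
- The unadjusted test uses the variance p(1−p).
- With balance inside centres, the true variance is W = [19p₁(1−p₁) + 18p₂(1−p₂)]/37.
- The true size is therefore 2·[1 − Φ(1.96/√R)], with R = W / [p(1−p)].

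| Centre rates | p(1−p) | W | R | True size |
|---|---|---|---|---|
| 70% / 70% | 0.2100 | 0.2100 | 1.000 | 5.0% |
| 80% / 60% | 0.2089 | 0.1989 | 0.952 | 4.5% |
| 90% / 50% | 0.2078 | 0.1678 | 0.808 | 2.9% |
| 95% / 45% | 0.2073 | 0.1448 | 0.699 | 1.9% |

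**3. The same by simulation** (40,000 runs, 1:1 within centre).

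| Centre rates | Pooled z | Centre-stratified Cochran-Mantel-Haenszel (CMH) |
|---|---|---|
| 80% / 60% | 4.5% | 5.0% |
| 90% / 50% | 3.0% | 5.1% |
| 95% / 45% | 2.1% | 5.1% |

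With no centre difference both are 4.8%. The SAP's own method, a crude logistic regression with a Wald test, is more conservative still in the three rows: 3.9%, 2.6% and 1.7%.

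**4. Power.** Take SA at 80% / 40% and GA at 98% / 82% by centre. The marginal rates are (19·0.80 + 18·0.40)/37 = 60.5% and (19·0.98 + 18·0.82)/37 = 90.2%, close to the design rates. Power is 88.7% unadjusted and 91.2% stratified, a loss of 2.5 points. With no centre difference both are 87.5%.

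**5. Logistic regression without and with centre** (6,000 runs per scenario, blocks of 4 or 6 within centre, Wald tests).

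| Centre log-odds difference | Size without / with (60% in both arms) | Power without / with (60% v 90%) |
|---|---|---|
| 0 | 0.044 / 0.046 | 0.853 / 0.859 |
| 0.5 | 0.040 / 0.043 | 0.858 / 0.868 |
| 1.0 | 0.038 / 0.047 | 0.864 / 0.879 |
| 1.5 | 0.032 / 0.048 | 0.863 / 0.891 |
| 2.0 | 0.029 / 0.052 | 0.876 / 0.910 |

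A log-odds difference of 1.0 means centre rates of about 71% and 48% in the SA arm; 2.0 means about 81% and 37%. Under the null, coverage of the crude 95% interval rises from 0.956 to 0.971, while with centre it stays between 0.948 and 0.957. The simulation error on a size near 0.05 is √(0.05·0.95/6,000) = 0.003. In the power scenarios 101 to 158 of the 6,000 runs could not be fitted and were left out for both models.

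**The case against.** The strongest reply is that the error runs only one way. A crude analysis cannot produce a false superiority claim, and if centre is not prognostic nothing is lost. The striking sizes of 3.0% and 2.1% need centre gaps of 40 and 50 points; a 20-point gap gives 4.5%. All of this stands, and it limits how serious the point is.

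Not all of the shortfall comes from centre. The crude Wald test has size 0.044 with no centre effect at all. That stands, but the further fall to 0.029 is due to centre, and the adjusted model does not show it.

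Adding centre does not narrow the odds-ratio interval. In a logistic model it raises the standard error of the log odds ratio: at a centre log-odds difference of 1.0, the median is 0.680 with centre and 0.640 without. The target changes too: the conditional odds ratio there is 6.46, the marginal one 6.00. This is correct. Too wide must therefore be read as over-coverage for the crude model's own target; the gain from adjustment is correct size and more power.

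The wording for the supporting model is open, so centre might enter there. That leaves the choice unfixed, and the primary model would still omit it.

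The SAP's rule for claiming superiority rests on an observed 30-point difference, which a model term would not alter. That is true but a separate matter; the logistic estimates and intervals remain the stated main analysis. Finally, the urinary-retention threshold says nothing direct about mobilisation. It shows only that practice differs between the sites.

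**Conclusion.** The concern holds for the THA and TKA trials. The stratification factor is missing from the primary model, from the named covariates of the supporting model and from the key secondary analyses.

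The effect is conservative and of modest size. Crude size lies between about 4.5% and 2.1% for assumed centre gaps of 20 to 50 points (pooled z), and the power loss at the design rates is about 0.6 to 3.4 points (logistic regression). These figures rest on assumed centre rates and on all 74 patients being analysed, before the 15% dropout the SAP allows for. If the centres do not differ, the cost of omitting centre is negligible. The change should be made because it is nearly free and aligns the analysis with the randomisation, not because the planned analysis could mislead in favour of GA.

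**What to change.** For the THA and TKA trials:

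- Include centre as a fixed effect in the main logistic model and keep the crude estimate as supportive. A Mantel-Haenszel risk difference stratified by centre is an alternative on the scale of the SAP's superiority rule. Name one as primary.
- State that the centre-adjusted odds ratio is conditional on centre, and say which odds ratio is the primary estimate.
- Replace the open list in the supporting model with a complete one.
- Define centre as the centre where the patient was randomised, including for envelope blocks moved between sites.
- Carry centre into the key secondary analyses: a linear model with centre or a van Elteren test for continuous outcomes, CMH for dichotomous ones, and a centre term in the mixed model for pain and PONV.

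The UKA analysis stays as it is. The cost is one model term, one degree of freedom and a few sentences in the SAP, settled before allocation is revealed to the analysts. The sample size does not change and no new data are needed.

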	 Standard primary arthroplasty procedure is evaluated not to be suitable
	 Women considered fertile but without sufficient birth control

RECRUITMENT, WITHDRAWAL AND FOLLOW-UP

Patients are pre-screened by the orthopaedic surgeons. At a standard preoperative physical examination 2-3 week prior to surgery, patients are asked whether research personnel can contact patients to provide them with study information. If patients consent to participation, the anaesthesiologist at the following standard preoperative anaesthesiologic examination will screen the patient for any contraindications for either SA or GA. Once screened by the anaesthesiologists, patients are considered included in the studies and baseline characteristics will be recorded.

Should the investigators become aware of previously unknown conditions, making included patients ineligible for participation, the investigators will withdraw the patient. These conditions include but are not limited to worsening of known disease, newly developed diseases or health conditions, and general safety concerns regarding anaesthesia.

In a CONSORT flow diagram the following will be reported; number of screened patients, number of excluded patients, number of randomized patients, number of patients allocated to each trial arm, number of patients that received anaesthesia in accordance with the allocation, and the number of patients that, after randomization, withdrew their consent, were excluded, or lost to follow-up.

BASELINE CHARACTERISTICS

The following baseline characteristics are registered at the time of inclusion:

Age, sex, height, weight, Charlson Comorbidity Index, Pain Catastrophizing Scale score, FRAILscale, ASA-score, preoperative blood sample results.

The baseline characteristics will be presented by intervention group using descriptive statistics. No statistical testing will be performed for baseline differences as suggested by the CONSORT-group [2].

ANALYSIS

OUTCOME DEFINITIONS

PRIMARY OUTCOME:

Ability to walk 5 meters 6 hours postoperatively:

Whether or not the participant is able to walk 5 meters safely and independently (also when using walking aid) within 6 hours of surgery evaluated by physiotherapists postoperatively.

Primary goal: Stable and safe 2-point gait with two crutches.

Secondary goal: Stable and safe 3-point gait with two crutches.

- Negative criteria:
 - Orthostatic: Dizziness, nausea, vomiting, fainting.

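### The primary result is planned only as crude and adjusted odds ratios, which differ in size without any confounding and are not on the scale of the SAP's 30-point superiority rule

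*SAP*

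**What the plan says.** Under Analysis methods, the SAP compares the proportions safely mobilised within 6 hours by logistic regression and names no covariate for that main model. It continues: "A supporting model adjusted, including possible confounders such as age and sex, will also be conducted". On reporting it says: "Estimates from the analysis will be presented as odd-ratios and 95% confidence intervals, for both crude and adjusted models". The mention of a crude model shows that the main model contains treatment only.

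The same section, and the Framework section, set the superiority rule as a difference in proportions of 30% in favour of GA. No difference in proportions with a confidence interval is listed among the estimates for the primary outcome.

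The data registered at inclusion are listed under Baseline characteristics: "Age, sex, height, weight, Charlson Comorbidity Index, Pain Catastrophizing Scale score, FRAILscale, ASA-score, preoperative blood sample results".

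The Sample size section is built on a "difference between 60% achieving safe mobilization in one group and 90% of achieving safe mobilization in the other group within 6 hours", which it says needs 32 patients per arm in each trial. The Trial design section describes each trial as a "pragmatic, multicentre, randomized (1:1), single-blinded, clinical trial".

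**The concern.** Three features of the primary outcome reporting do not fit together.

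1. **The reason given for adjusting.** Randomisation removes systematic confounding by age, sex or frailty. The reason to adjust for baseline predictors in a trial is precision. Describing the covariates as possible confounders suggests that the adjusted result is the corrected one.
2. **Two odds ratios side by side.** The crude odds ratio is a marginal quantity and the adjusted one is conditional on the covariates. The odds ratio is non-collapsible, so when the covariates predict the outcome the true conditional value lies further from 1 than the marginal one, even under perfect balance. Under the confounder label, a reader could take that gap for bias removed.
3. **The scale.** The decision rule is a difference in percentage points. An odds ratio does not determine that difference unless the rate in one arm is also given.

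What is at stake is how the primary result is read and whether it can be set against the SAP's own rule. The validity of the main test is not in question.

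**Working it through.** **Inputs.** From the SAP: 60% and 90%, 95% confidence, 80% power, 32 per arm, 1:1 allocation, 30-point rule, and 30–45% safely mobilised after SA in previous studies. Not in the SAP: how strongly the covariates predict the outcome. This is an assumption and is varied below. β denotes the log odds ratio per standard deviation of a combined covariate score.

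**1. The SAP's own figure.** Two-proportion formula, two-sided 5%, pooled variance under the null, no continuity correction:

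n = [1.96·√(2·0.75·0.25) + 0.842·√(0.6·0.4 + 0.9·0.1)]² / 0.30² = 31.5, so 32 per arm.

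This reproduces the stated number (power at 32 is 80.6%). The calculation is unadjusted, so the crude main analysis is the one the trial was sized for.

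**2. Crude odds ratio.** (0.9/0.1) / (0.6/0.4) = 9/1.5 = 6.0.

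**3. Conditional odds ratio for the same effect.** Take a standard normal score Z with the same distribution in both arms, so that there is no confounding. For each arm, solve E[expit(a + βZ)] = p for the intercept a, with p = 0.6 (SA) and p = 0.9 (GA), by numerical quadrature. The conditional odds ratio is exp(a_GA − a_SA).

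| β | OR per SD | a_SA | a_GA | Conditional OR |
|---|---|---|---|---|
| 0 | 1.0 | 0.405 | 2.197 | 6.0 |
| 0.5 | 1.65 | 0.429 | 2.295 | 6.5 |
| 1.0 | 2.7 | 0.490 | 2.564 | 8.0 |
| 1.4 | 4.1 | 0.555 | 2.868 | 10.1 |
| 1.5 | 4.5 | 0.572 | 2.953 | 10.8 |

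The rates are 60% and 90% in every row. The odds ratio changes only because it is conditional.

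**4. Odds ratio against the 30-point rule.** Hold the crude odds ratio at 6.0 and vary the SA rate over values the SAP mentions:

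- SA 60%: odds 1.5 × 6 = 9.0, GA 90%, difference 30 points.
- SA 45%: odds 0.818 × 6 = 4.91, GA 83%, difference 38 points.
- SA 30%: odds 0.429 × 6 = 2.57, GA 72%, difference 42 points.

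One odds ratio therefore corresponds to differences of 30 to 42 points.

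**5. What adjustment would do to power.** Expected failures at 32 per arm: 32 × 0.4 + 32 × 0.1 = 12.8 + 3.2 = 16. Simulated trials of 32 per arm (3,000 or 4,000 runs per setting), crude model against a model with three covariates:

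| β | Odds ratio, Wald | Odds ratio, likelihood ratio | Difference, crude vs standardised |
|---|---|---|---|
| 0 | 77% vs 76% | 83% vs 82% | 84% vs 83% |
| 0.5 | 77% vs 78% | 84% vs 85% | 85% vs 84% |
| 1.0 | 77% vs 82% | 83% vs 88% | 84% vs 88% |
| 1.4 | 75% vs 83% | 82% vs 90% | gain of up to 6 points |

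A separate run of the standardised difference with useless covariates gave 85% falling to 83%. Its variance efficiency relative to the crude difference, in a run with three equally predictive covariates, was 0.95, 0.98, 1.10 and 1.22 at β of 0, 0.5, 1.0 and 1.5.

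**6. Error rate.** With no treatment effect, the adjusted Wald test of the odds ratio had a size of 4.4–5.0% at 75% in both arms. The standardised difference with a model-based standard error ran at about 6–8%, and the crude difference at 5.8–6.9%. With so few failures, the standard error method has to be chosen with care.

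**The case against.** The strongest case on the other side is that nothing here is wrong as analysis. An unadjusted comparison of a randomised binary endpoint is valid, it matches the sample size calculation, and the SAP ranks the models clearly, so the open covariate list does not leave the main result open to choice. With about 16 failures, some 3 of them under GA, keeping a multi-covariate model as supporting is defensible. At the 95% GA rate the SAP cites from previous studies, an arm of 32 would have no failure at all in 0.95³² = 19% of trials. All of this stands.

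A reader might infer that the SAP gives up precision and ought to make the adjusted model primary. The documents do not support that. They give no prognostic strength for any covariate, and the eligibility criteria exclude users of a walker or wheelchair and residents of institutions, which may narrow the range of frailty. With weak predictors there is no gain, and with useless ones there is a small loss.

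Three further inferences also go too far:

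- **That the two odds ratios cannot be compared at all.** Direction and test result can be; only the magnitudes cannot be equated.
- **That the adjusted odds ratio will always look stronger.** In simulated trials it fell below the crude one in 28%, 22% and 12% of runs at β of 0, 0.5 and 1.0.
- **That the covariates are complete for every patient.** The SAP says only that they are registered at inclusion.

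The SAP does not itself claim that a gap between the odds ratios shows confounding. Its wording merely invites that reading.

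**Conclusion.** The point holds as one about estimate, scale and description. The crude and adjusted odds ratios target different quantities: 6.0 against about 6.5 to 10 at the SAP's planning rates, for mildly to strongly predictive covariates and no confounding. That range rests on an assumed normal covariate score and on prognostic strengths the SAP does not give; with non-predictive covariates the true values coincide. Neither odds ratio is on the scale of the 30-point rule, and this part needs no assumption about the covariates.

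The primary analysis itself can stay as it is. Moving to the adjusted model would change power by about nothing with weak predictors and by roughly 4 to 8 points with moderate to strong ones, so it is a trade-off for the sponsor. The open covariate list alone would be a missing detail in a supporting analysis. It matters here because a standardised estimate needs a fixed model. Overall this is a cheap improvement to the reporting of the primary outcome.

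**What to change.** In Analysis methods, main analysis of the primary outcome:

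1. Report the GA minus SA difference in proportions with a 95% CI for the main analysis. The crude odds ratio may stay beside it.
2. Give the adjusted result as a standardised (marginal) difference in proportions with a 95% CI, from one short model fixed in advance on baseline data already recorded. Age, sex and FRAIL scale, one term each, would be an example; the SAP offers no basis for preferring FRAIL over ASA or Charlson, so the sponsor should choose and state it.
3. Name a standard error or bootstrap method suited to about 16 expected failures.
4. Replace the phrase about possible confounders with a statement that adjustment is for precision, and add that crude and conditional odds ratios are not to be equated in magnitude.
5. Optionally, make the adjusted model primary if the sponsor expects at least moderately predictive covariates, and state this before the data are analysed.

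Cost: SAP wording, a few lines of R and slightly more analysis work, with no new data and no more patients. The adjusted estimate may lose up to about 2 points of power if no covariate predicts the outcome. While the crude analysis stays primary, that loss does not touch the main result.

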If one centre experiences recruitment issues, randomisation envelopes in 1 or 2 blocks will be transferred to the other centre.

FRAMEWORK

Superiority of GA over SA in achieving safe mobilization within 6 hours of surgery will be claimed if a difference in proportions of 30% is found in favour of GA.

STATISTICAL INTERIM ANALYSES AND STOPPING GUIDANCE

No interim analyses are planned. The investigators will evaluate the occurrence of serious adverse events, and if these occur in an unexpectedly high proportion of patients in relation to one of the interventions, the study will be stopped.

TIMING OF FINAL ANALYSIS

The final analysis is conducted when all included patients in the trial have passed the last followup (30 days after surgery).

TIMING OF OUTCOME ASSESSMENTS

Primary endpoint: safe mobilization at 5-meter walking test within 4-6 hours postoperatively. Patients will be given until 6 hours postoperatively to complete the walking test, and any early failed attempts will be redone at 6 hours postoperatively.

Secondary endpoints: fulfilment of discharge criteria, postoperative nausea and vomiting, pain, and use of opioids are evaluated at 4 and 6 hours postoperatively on the day of surgery and at 10:00 and 18:00 on any following postoperative days if the patient is still admitted.

STATISTICAL PRINCIPLES

CONFIDENCE INTERVALS AND P-VALUES

Confidence level is set at 95%, and results are presented with 95% confidence intervals. No adjustments for multiplicity are made.

ADHERENCE AND PROTOCOL DEVIATIONS

If patients are anaesthetised differently than allocated (i.e., GA instead of SA, due to technical difficulties), this is registered, and data collection continues. Reasons for cross-over are registered and reported. The overall adherence within the intervention groups will be reported.

All protocol deviations regarding sample size, eligibility, randomization, intervention, outcome definitions and statistical analyses plan will be reported.

ANALYSIS POPULATIONS

Any cases of crossover between the intervention groups will be included in their allocated treatment group as part of a modified intention-to-treat (mITT) analysis. The mITT will exclude randomised patients that did not undergo the intended arthroplasty surgery in the SAGA setup:

- Patients that after randomisation, but before being told their treatment allocation, decided not to go through with the arthroplasty surgery at the hospital.

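### The primary odds ratio has no finite estimate or interval if every GA patient in a trial succeeds, and the SAP plans no fallback and names no test

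*SAP*

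**What the plan says.** Under Analysis Methods, the proportions safely mobilised within 6 hours "will be compared between intervention groups using a logistic regression model", and "Estimates from the analysis will be presented as odd-ratios and 95% confidence intervals, for both crude and adjusted models". The adjusted model adds covariates such as age and sex. The type of test (Wald, score or likelihood ratio) and the type of interval are not named. Fisher's exact test is planned only for key secondary dichotomous outcomes. The software is R.

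Framework and Analysis Methods also state that superiority of GA is claimed if a 30% difference in proportions in its favour is found. No interval or test is attached to that difference.

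Under Sample Size, the SAP reports that in previous studies "safe mobilization was achieved after GA for 95% of THA and TKA patients", against 30-45% after SA. It plans on "a clinically relevant difference between 60% achieving safe mobilization in one group and 90% of achieving safe mobilization in the other group", which gives 32 per arm at 95% confidence and 80% power, and recruits 37 per arm to allow for dropout. Each of the three trials stands alone.

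**The concern.** A maximum-likelihood odds ratio does not exist when one arm has no failures. The arms are small, and the success rate that the SAP cites for GA is close to 1, so an arm of 32 to 37 patients without a failure is a realistic outcome. The only planned primary estimate would then be unusable in the very result most favourable to GA. Adding age and sex does not help, because the treatment coefficient still diverges.

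Two further consequences follow.

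- Any penalised, exact or score method chosen after seeing such data would be a post-hoc change to the primary analysis.
- The Missing Data section compares conclusions across three ways of handling missing outcomes. If all observed GA patients succeed, a Wald test on available data shows nothing. Counting one missing GA patient as a failure, which is less favourable to GA, could then make the result significant. The conclusions would differ because of the method and not because of the data.

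**Working it through.** **Inputs.** From Sample Size: 60% vs 90%, 95% confidence, 80% power, 32 evaluable and 37 recruited per arm, and cited GA success of 95% and SA success of 30-45%. Allocation is 1:1 (Trial Design). Sidedness is not stated; two-sided 5% is assumed, since one-sided gives 25 per arm and two-sided gives the SAP's 32.

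**1. The plan's own figure.** The pooled two-proportion formula, with mean proportion 0.75, is

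n = [1.96·√(2·0.75·0.25) + 0.8416·√(0.6·0.4 + 0.9·0.1)]² / 0.30²
= [1.2002 + 0.4835]² / 0.09 = 2.835 / 0.09 = 31.5, so 32 per arm.

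The stated sample size is reproduced. It belongs to the score (Pearson chi-square) test.

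**2. Chance that no GA patient fails, per trial (pⁿ).**

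| GA success | n = 32 | n = 37 |
|---|---|---|
| 95% (cited) | 0.95³² = 19.4% | 0.95³⁷ = 15.0% |
| 90% (planning) | 0.90³² = 3.4% | 0.90³⁷ = 2.0% |

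**3. What the planned model then returns.** Take GA 32/32 and SA 20/32. R's glm gives a log odds ratio of about 19 with standard error about 1901 and Wald p = 0.99. The Wald interval runs from 0 to infinity, and the upper profile limit is NA. The score statistic on the same data, with pooled proportion 52/64 = 0.8125, is 0.375² / (0.8125·0.1875·2/32) = 14.8, p = 0.0001.

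With one GA failure (31/32 vs 20/32) the Wald test works again: log odds ratio = ln 31 − ln(20/12) = 2.923, SE = √(1/31 + 1/1 + 1/20 + 1/12) = 1.080, z = 2.71, p = 0.007. A slightly worse GA result moves the Wald p-value from 0.99 to 0.007.

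**4. What the risk difference returns on the separated data.** The difference is 100% − 62.5% = 37.5 points. The Wilson limits are 0.893 to 1 for GA and 0.453 to 0.771 for SA. Newcombe's limits are

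- lower: 0.375 − √[(1 − 0.893)² + (0.771 − 0.625)²] = 0.19
- upper: 0.375 + √[(1 − 1)² + (0.625 − 0.453)²] = 0.55

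The interval is finite and usable: 19 to 55 points.

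**5. The 30% rule in separated outcomes.** Read as an observed difference of at least 30 points, with GA at 100% the rule needs SA success of at most 70%. At 37 per arm that is at most 25 of 37. The binomial probability is 99.8% if true SA success is 45%, and 86.7% if it is 60%.

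**6. Exact power** (all 2×2 outcomes enumerated; Wald counted as non-significant under separation).

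| Setting | Wald | Score |
|---|---|---|
| 60% vs 90%, n = 32 | 77.0% | 82.8% |
| 60% vs 90%, n = 37 | 83.8% | 87.5% |
| 45% vs 95%, n = 32 | 80.5% | 99.9% |
| 45% vs 95%, n = 37 | 85.0% | >99.9% |

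The likelihood-ratio test also has 82.8% at 60% vs 90%, n = 32. If it replaces Wald only in the separated outcomes of that setting, power is 80.4%, so most of the Wald shortfall is the separation problem again.

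**7. Type I error, n = 32.** At 90% in both arms: Wald 1.1%, score 5.6%, likelihood ratio 7.2%. At 95% in both arms the likelihood ratio has 8.6%.

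**The case against.** The strongest reply is that the superiority claim does not rest on the odds ratio. The SAP's rule uses a difference in proportions, which stays finite at 100% success and is met in about 87% to 99.8% of separated outcomes (step 5). A reader might infer that the best possible GA result would have to be declared non-significant. The document does not support that: the claim would usually survive. What fails is the odds ratio, its interval and any Wald p-value. What remains of the concern is that the surviving difference would be reported with no planned measure of uncertainty.

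A reader might also infer that the trials miss their stated 80% power. The document does not support that either. It never names the Wald test; that is only what R's glm summary prints by default. The score test, to which the sample size belongs, has 82.8% at 32 per arm, and even Wald has 83.8% if all 37 are evaluable. The defect is an unnamed test, not a wrong sample size.

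Finally, the 95% comes from previous THA and TKA studies. The SAP plans on 90%, where separation is rare, and gives no rate for UKA. This stands, and it limits the size of the point. A crude odds ratio is also a conventional choice in itself; the gap is the missing fallback.

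**Conclusion.** The point holds as a cheap improvement, not as an error that invalidates the design. As written, the plan can leave a trial without a usable primary estimate. The probability per trial is 15-19% if GA success is 95%, as cited for THA and TKA, and 2-3% if it is 90%, as planned. These figures assume independent patients and 32 to 37 evaluable per arm. The sample size of 32 is correct for the score test. The possible 3-point power shortfall applies only if a two-sided Wald test is used with about 32 evaluable per arm.

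**What to change.** In Analysis Methods, for the primary outcome:

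- Report the risk difference with a score-type 95% CI (Miettinen-Nurminen or Newcombe). This also gives an interval to the difference on which superiority is claimed.
- Take the primary p-value from the score (Pearson chi-square) test. This matches the sample-size formula. Do not use Wald, which fails under separation, or likelihood ratio, whose type I error is 7-9% at 90-95% success.
- Keep the crude and adjusted odds ratios as supporting measures, with Firth-penalised logistic regression if an arm has no failures.

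The cost is SAP wording and a few lines of R, with no new data or patients. The downsides are one more estimate to report and a score-test type I error slightly above 5% in some settings (5.6% at 90% in both arms, n = 32).
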